2.2.3. Additional Estimand(s)

[figure not shown]
CCI

CCI

CCI

- CCI
-
-
-
-
-
-
-
-
-

2.3. Study Design

This is a Phase 3, randomized, observer-blinded study to evaluate the efficacy, safety, tolerability, and immunogenicity of qIRV-encoding HA of 4 seasonally recommended strains (2 A strains and 2 B strains) in healthy individuals ≥ 18 years of age.

Up to approximately 36,200 participants will be enrolled in this study and stratified by age as follows:

- Up to approximately **CCI** participants ≥ 65 years of age will be enrolled and randomized **CC** to receive 1 dose of either qIRV or seasonal QIV comparator.
- Up to approximately **CCI** participants 18 through 64 years of age will be enrolled and randomized **CC** to receive 1 dose of either qIRV or seasonal QIV comparator. Enrollment of participants 18 through 64 years of age is contingent on obtaining satisfactory Phase 1/2 data in participants of this age and will only proceed if regulatory authority endorsement is obtained to do so. Enrollment into each of the 2 age strata (18 through 64 years of age and ≥ 65 years of age) may therefore occur independently. The qIRV dose level per strain to be used will be based on Phase 2 safety and immunogenicity data and will be detailed in the IPM; the qIRV dose level may differ by age stratum.
- In each age stratum:
 - Approximately **CCI** participants will be included in a reactogenicity subset. For participants in the reactogenicity subset, a reactogenicity e-diary will be completed by each participant for 7 days following vaccination.
 - Approximately **CCI** participants will be included in an immunogenicity subset. Blood samples of approximately 15 mL will be collected for immunogenicity assessments prior to vaccination and at 4 weeks and 6 months after vaccination. An additional optional blood sample of 50 mL may be collected from participants who consent to the time points for assessment of **CCI**; the number of participants asked to provide these samples will be determined by Pfizer, contingent on operational considerations. Approximately **CCI** participants ≥ 18 years of age will be asked to consent to alternatively providing 50-mL, rather than 15-mL, blood samples at the same time points, which will be used for immunogenicity assessments as well as assay development.
 - Participants may be enrolled in either or both of the subsets described above.

Efficacy will be assessed in this study through surveillance for ILI. Following vaccination, all participants will be prompted approximately weekly to complete a questionnaire, using an e-diary or equivalent technology, designed to identify ILI. This questionnaire will also be completed any time the participant develops symptoms of ILI. If a participant develops ILI, 2 midturbinate swabs will be collected (1 from each nostril), either by the participant or by site staff at an ILI visit. These swabs will then undergo RT-PCR and culture testing at a

central laboratory to confirm the presence of influenza virus. Culture testing will only be conducted on swab samples from participants with an RT-PCR-positive swab sample from the corresponding ILI visit. Surveillance for ILI will continue until each influenza season ends (as judged by Pfizer based on epidemiological data).

If enrollment is insufficient, or it is projected that insufficient first-episode LCI cases associated with per-protocol ILI, caused by any strain, will accrue during the northern hemisphere 2022-2023 influenza season (as judged by Pfizer), this study may be extended into a second influenza season within the southern hemisphere.

CCI

Of these

additional participants:

- The number of participants 18 through 64 years of age or ≥ 65 years of age will be determined by Pfizer based on enrollment in each of these age strata during the northern hemisphere 2022-2023 influenza season and/or projected LCI case accrual in each age stratum.
- Up to approximately CCI participants in each age stratum will be included in a reactogenicity subset. For participants in the reactogenicity subset, a reactogenicity e-diary will be completed by each participant for 7 days following vaccination.
- Up to approximately CCI participants in each age stratum will be included in an immunogenicity subset. Blood samples of approximately 15 mL will be collected for immunogenicity assessments prior to vaccination and 4 weeks and 6 months after vaccination.

The primary efficacy analysis may be conducted in each age stratum when at least CCI first-episode evaluable LCI cases associated with per-protocol ILI, caused by any strain, have been accrued in a given age stratum. Hence, the primary efficacy analysis in each age stratum may be conducted at different times and the hypothesis testing across the 2 age strata will be independent. Within each age stratum, hypothesis testing relating to the VE and immunogenicity objectives will occur in a hierarchical manner, as described in [Section 5.1.3](#).

3. ENDPOINTS AND BASELINE VARIABLES: DEFINITIONS AND CONVENTIONS

3.1. Primary Endpoint(s)

3.1.1. Primary Efficacy Endpoint

- First-episode LCI cases with associated per-protocol ILI, caused by any strain, at least 14 days following vaccination.

3.1.1.1. LCI Case Derivation With Associated Per-Protocol ILI

To meet the requirement of LCI case definition with per-protocol ILI, an ILI (new onset or worsening of preexisting condition) should have at least 1 respiratory symptom concurrently with at least 1 systemic symptom and confirmed through RT-PCR or culture testing at the central laboratory (ie, positive result for any strain). The respiratory symptoms and systemic symptoms are listed below:

Respiratory symptoms (ongoing for at least 12 hours, or multiple episodes within a 24-hour period):

- CCI
- [REDACTED]
- [REDACTED]
- [REDACTED]
- [REDACTED]
- [REDACTED]

Systemic symptoms:

- CCI
- [REDACTED]
- [REDACTED]
- [REDACTED]
- [REDACTED]
- [REDACTED]

The 2 midturbinate swabs will be collected for testing at a central laboratory using RT-PCR and viral culture testing to detect influenza viruses in the respiratory specimen. Culture testing will only be conducted on swab samples from participants with an RT-PCR-positive swab sample from the corresponding ILI visit. The ILI visit (site, telehealth, home health) and swab samples should be done from the concurrent respiratory and systemic symptom start date and up to 5 days after the participant no longer meets the per-protocol ILI

definition. The symptoms presented and initial symptom onset date are recorded at an ILI visit.

3.1.1.2. First-Episode LCI Case Derivation With Associated Per-Protocol ILI

For the primary efficacy endpoint, only first-episode LCI cases with per-protocol ILI, with initial symptom onset date between Day 15 (ie, 14 days after vaccination) and the end of the influenza season (all inclusive), or the data cutoff date for performing primary efficacy analysis as determined by the sponsor, will be considered. Additionally, if there are any important protocol deviations before/during ILI onset, the cases from these ILIs will not be included in the evaluable efficacy population analysis.

The important protocol deviations are identified throughout the study via study monitor, medical, and other team member review. In the case in which there are multiple episodes of LCI with per-protocol ILI, only the first-episode that is between Day 15 and the end of the influenza season, or the data cutoff date for performing primary efficacy analysis as determined by the sponsor, will be included as the primary endpoint.

Following the ILI visit being initiated, if new OR recurrent symptoms that meet per-protocol requirements for an ILI visit emerge, there is no minimum time between symptom start and/or resolution that would preclude an additional ILI visit. Investigators should discuss the symptoms with the participant and use their clinical judgment to determine if such new OR recurrent symptoms are part of a single ILI or a second ILI, and therefore if an additional ILI visit is required.

3.1.2. Primary Safety Endpoint

- Local reactions for up to 7 days following vaccination.
- Systemic events for up to 7 days following vaccination.
- AEs through 4 weeks after vaccination.
- SAEs through 6 months after vaccination.

It has been requested by the regulatory agency to combine reactogenicity data from different sources, such as the e-diary and AE CRF. Since the AE CRF does not designate a specific page to collect reactogenicity data that are missing from the e-diary, Pfizer has adopted a process of providing a listing of AEs reported within 7 days after vaccination to the clinical team to review/query the AEs and flag the preferred terms that should be considered as reactogenicity events before the database is locked. AEs reported on the same day of vaccination, but missing AE start times are defaulted to AEs after vaccination. Only those AEs reported within 7 days with completed AE start dates after vaccination, matched with the flagged preferred terms, will be pooled with reactogenicity data from the e-diary. If the same reactogenicity event is reported on the same day from both the e-diary and AE CRF, the highest grade from the 2 data sources will be used for that specific day.

It should be noted that the data collection in the AE CRF is different from that in the e-diary:

- For redness, swelling, and fever, the measured size and temperature are recorded in the e-diary, but not in the AE CRF. Therefore, the maximum grading for the 3 items reported in the e-diary will be based on actual size and FDA toxicity grading scale, but the maximum grading of the 3 reactogenicity terms from the AE CRF will be based on the grading scale in the CRF page. Across the 7 days, only the maximum grading from both sources will be used for the aggregated severity analysis, though the grading algorithm is different between the 2 data sources.
- For pain at the injection site and all systemic events, the severity grading algorithm in the e-diary and AE CRF may not be the same; the highest severity grade will be used.
- Both related and nonrelated solicited reactogenicity events that are recorded on the AE CRF will be included.
- If a participant did not have any e-diary data transferred, the AE CRF data will not be used for derivation because the AE CRF is considered as “supplemental” for reactogenicity data missed on certain days but not all 7 days. In other words, if a participant did not report any e-diary data, the participant will not be included in the reactogenicity population.

Related and nonrelated reactogenic SAEs will be presented in both reactogenicity and AE tables. Immediate AEs and AEs leading to discontinuation, as well as reactogenicity AEs for participants not in the reactogenicity population, will be summarized with the AE tables.

In addition, a separate reactogenicity analysis will also be performed without combining any reactogenicity data collected from the AE CRF.

3.1.2.1. Local Reactions

The local reactions reported in the e-diary are redness, swelling, and pain at the injection site, from Day 1 through Day 7 after vaccination, where Day 1 is the day of vaccination. This section describes derivations with details for the assessment of local reactions: presence, maximum severity level, duration, and onset day of local reactions, in addition to presence of severe local reactions on each day.

Presence or Absence

For the data summary of the presence (yes or no) of a local reaction during the interval from Day 1 through Day 7 after each vaccination, where Day 1 is the day of vaccination, the following variables are required to compute the proportions:

- Presence (yes or no) of each severe/Grade 4 local reaction on each day and any day (Day 1 through Day 7).

- Presence (yes or no) of each local reaction, by maximum severity on any day (Day 1 through Day 7).

For each local reaction and any local reaction on any day, Table 3. and Table 4, respectively, explain the algorithm to derive the presence of a reaction (yes or no) during the interval from Day 1 through Day 7, where Day 1 is the day of vaccination.

Table 3. Derived Variables for Presence of Each Local Reaction Within 7 Days After Vaccination

Variable ^a	Yes (1)	No (0)	Missing (.)
Presence of each local reaction	Participant reports the reaction as “yes” on any day (Day 1 through Day 7)	Participant reports the reaction as “no” on all 7 days (Day 1 through Day 7) or as a combination of “no” and missing on all 7 days (Day 1 through Day 7)	Participant does not report any data on all 7 days (Day 1 through Day 7) for the reaction

a. The variables will be derived for each of the local reactions (redness, swelling, and pain at the injection site) and for each of the severe local reactions within the interval from Day 1 through Day 7 after vaccination.

Table 4. Derived Variables for Presence of Any Local Reaction Within 7 Days After Vaccination

Variable ^a	Yes (1)	No (0)	Missing (.)
Presence of any local reaction	Participant reports any local reaction as “yes” on any day (Day 1 through Day 7)	For all 3 local reactions, participant reports “no” on all 7 days (Day 1 through Day 7) or as a combination of “no” and missing on all 7 days (Day 1 through Day 7)	Participant does not report any data for all 3 local reactions on all 7 days (Day 1 through Day 7)

a. The variables will be derived for any of the local reactions (redness, swelling, and pain at the injection site) and for any of the severe local reactions within the interval from Day 1 through Day 7 after vaccination.

Variables for the presence of each local reaction and presence of any local reaction will be similarly derived as in Table 3 and Table 4 when combining local reaction data from the AE CRF and e-diary data.

Severity and Maximum Severity

Redness and swelling will be measured and recorded in measuring CCI [REDACTED] and then categorized during analysis as absent, mild, moderate, or severe, based on the grading scale in Table 5 with combined local reaction data from both the e-diary and AE CRF. For the local reaction analysis, without combining local reaction data from the AE CRF, a similar grading scale as Table 5 (without AE CRF data) will be used. CCI [REDACTED]

[REDACTED] Pain at the injection site will be assessed by the participant as absent, mild, moderate, or severe according to the grading scale in Table 5.

Table 5. Local Reaction Grading Scale

	Mild (Grade 1)	Moderate (Grade 2)	Severe (Grade 3)	Potentially Life-Threatening (Grade 4) ^a
Pain at the injection site	Does not interfere with activity (from the e-diary) or mild from the AE CRF	Interferes with activity (from the e-diary) or moderate from the AE CRF	Prevents daily activity (from the e-diary) or severe from the AE CRF	Emergency room visit or hospitalization for severe pain Or life-threatening from the AE CRF
Redness	2.0 cm to 5.0 cm CCI [REDACTED] [REDACTED] or mild from the AE CRF	>5.0 cm to 10.0 cm CCI [REDACTED] [REDACTED] or moderate from the AE CRF	>10 cm CCI [REDACTED] [REDACTED] or severe from the AE CRF	Necrosis or exfoliative dermatitis Or life-threatening from the AE CRF
Swelling	2.0 cm to 5.0 cm CCI [REDACTED] [REDACTED] or mild from the AE CRF	>5.0 cm to 10.0 cm CCI [REDACTED] [REDACTED] or moderate from the AE CRF	>10 cm CCI [REDACTED] [REDACTED] or severe from the AE CRF	Necrosis Or life-threatening from the AE CRF

a. Only an investigator or qualified designee is able to classify a participant's local reaction as Grade 4, after clinical evaluation of the participant or documentation from another medically qualified source (eg, emergency room or hospital record). Grade 4 local reactions will be collected on the AE case report form and assessed by the investigator using the AE intensity grading scale.

For each local reaction reported for each vaccination, the maximum severity grade will be derived for the e-diary collection period (Day 1 through Day 7, where Day 1 is the day of each vaccination) as follows:

maximum severity grade = highest grade (maximum severity) within 7 days after vaccination (Day 1 through Day 7) among severity grades where the answers are neither "no" nor missing for at least 1 day during the interval from Day 1 through Day 7.

Duration of Each Local Reaction (First to Last Day Reported)

For participants experiencing any local reactions (or those with a derived reaction as described in [Table 4](#)), the maximum duration (resolution date of reaction - start date of reaction + 1) will be derived for each study vaccination.

Resolution of the reaction is the last day on which the reaction is recorded in the e-diary or AE CRF, or if it is unresolved during the participant e-diary recording period, the date the reaction ends (end date collected on the CRF) or AE stop date, whichever is longer, unless chronicity is established. If there is no known end date, the duration will be considered unknown and set to “missing.” Participants with no reported reactions have no duration.

Onset Day of Each Local Reaction

The onset day of each local reaction will be derived. Onset day is defined as the first day of reporting any severity.

- For the onset day of each local reaction, if participants report a change in severity of the local reaction, only the first day of reporting that specific local reaction will be counted.

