To demonstrate that the efficacy of qIRV is superior to that of QIV against LCI associated with per-protocol ILI, in participants 18 through 64 years of age	
In participants <math>\geq 18</math> through 64 years of age complying with the key protocol criteria (evaluable participants) at least 14 days after study intervention:
 
 
• RVE, defined as the relative reduction of the proportion of participants reporting LCI cases with associated per-protocol ILI in the qIRV group compared to the QIV group
 
	First-episode LCI cases with associated per-protocol ILI caused by any strain
Primary Safety:  To define the safety and tolerability profile of qIRV, in participants 18 through 64 years of age and $\geq 65$ years of age	
Primary Safety:
 
In participants 18 through 64 years of age and <math>\geq 65</math> years of age separately, receiving study intervention, the percentage of participants reporting:
 
 
• Local reactions for up to 7 days following vaccination
 
• Systemic events for up to 7 days following vaccination
 
 
In participants 18 through 64 years of age and <math>\geq 65</math> years of age separately and combined, receiving study intervention, the percentage of participants reporting:
 
 
• AEs through 4 weeks after vaccination
 
• SAEs through 6 months after vaccination
 
	
Primary Safety:
 
 
• Local reactions (pain at the injection site, redness, and swelling)
 
• Systemic events (fever, fatigue, headache, chills, vomiting, diarrhea, new or worsened muscle pain, and new or worsened joint pain)
 
• AEs
 
• SAEs
 

Objectives	Estimands	Endpoints
Secondary Efficacy:  To evaluate the efficacy of qIRV compared to QIV against LCI or CCI associated with different definitions of ILI, in participants 18 through 64 years of age and $\geq 65$ years of age	Secondary Efficacy:  In participants 18 through 64 years of age and $\geq 65$ years of age separately, complying with the key protocol criteria (evaluable participants) at least 14 days after study intervention:	Secondary Efficacy:

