#### **8.3.4.2. Local Reactions**

During the reactogenicity e-diary reporting period, participants will be asked to assess redness, swelling, and pain at the injection site and to record the symptoms in the reactogenicity e-diary. If a local reaction persists beyond the end of the reactogenicity e-diary period following vaccination, the participant will be requested to report that information and the corresponding resolution date. The investigator will enter this resolution date in the CRF.

Participants will be provided with a measuring device. Redness and swelling will be measured and recorded in **CCI** and then categorized during analysis as absent, mild, moderate, or severe based on the grading scale in [Table 2](#).

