**Table 2. Local Reaction Grading Scale**

	Mild (Grade 1)	Moderate (Grade 2)	Severe (Grade 3)	Potentially Life-Threatening (Grade 4)
Pain at the injection site	Does not interfere with activity	Interferes with activity	Prevents daily activity	Emergency room visit or hospitalization for severe pain
Redness	>2.0 cm to 5.0 cm CCI	>5.0 cm to 10.0 cm CCI	>10 cm CCI	Necrosis or exfoliative dermatitis
Swelling	>2.0 cm to 5.0 cm CCI	>5.0 cm to 10.0 cm CCI	>10 cm CCI	Necrosis

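### The visible centimetre lower bound for mild redness and swelling differs between protocol Table 2 and SAP Table 5, so a reading of exactly 2.0 cm grades as absent under one and mild under the other

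*SAP*

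**What the plan says.** Redness and swelling belong to the primary safety endpoint. Protocol Section 3 lists "Local reactions (pain at the injection site, redness, and swelling" among the primary safety endpoints, and SAP Section 2.2 carries the same list.

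The reactogenicity subset measures both reactions in the e-diary, and the grade is assigned afterwards. In protocol Section 8.3.4.2 the measurements are "categorized during analysis as absent, mild, moderate, or severe based on the grading scale in" Table 2. In SAP Section 3.1.2.1 they are "categorized during analysis as absent, mild, moderate, or severe, based on the grading scale in Table 5". SAP Section 3.1.2 adds that e-diary grading of these items "will be based on actual size and FDA toxicity grading scale".

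The mild cells differ. Protocol Table 2 has ">2.0 cm to 5.0 cm CCI" in both the redness and the swelling row. SAP Table 5 has "2.0 cm to 5.0 cm CCI [REDACTED] [REDACTED] or mild from the AE CRF" in both rows. The next SAP column reads ">5.0 cm to 10.0 cm CCI [REDACTED] [REDACTED] or moderate from the AE CRF", so the greater-than sign is used elsewhere in the same rows.

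For the analysis without adverse event form data, SAP Section 3.1.2.1 says that "a similar grading scale as Table 5 (without AE CRF data) will be used".

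**The concern.** The lower bound of mild is the line between no reaction and a reaction. If the two documents place 2.0 cm on opposite sides of it, two programmers working from different documents could derive different values of a primary safety variable from the same diary record.

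The SAP does not present this as a change. Its version history says that version 3 follows protocol Amendment 4, and SAP Section 2.1 reserves major changes to primary endpoint definitions for a protocol amendment. Nothing in either document explains a different bound. Nor does the SAP shift lower bounds as a general convention: fever starts at 38.0°C inclusive in both protocol Table 4 and SAP Table 7.

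At stake are the reported proportions with redness or swelling, the mild segment of the severity bar charts, and the onset and duration summaries. No success criterion is involved.

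**Working it through.** Neither document gives a figure to reproduce here, because the point is a category boundary. The check is to code both scales as printed and compare them.

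Inputs, for a reading x in cm:

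| Grade | Protocol Table 2 | SAP Table 5 |
|---|---|---|
| Absent (implied) | x ≤ 2.0 | x < 2.0 |
| Mild | 2.0 < x ≤ 5.0 | 2.0 ≤ x ≤ 5.0 |
| Moderate | 5.0 < x ≤ 10.0 | 5.0 < x ≤ 10.0 |
| Severe | x > 10 | x > 10 |

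The recording unit is redacted, so three step sizes were assumed, each covering 0 to 12 cm:

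| Step (assumed) | Readings compared (12/step + 1) | Readings graded differently |
|---|---|---|
| 0.1 cm | 121 | 1, at 2.0 cm (absent / mild) |
| 0.5 cm | 25 | 1, at 2.0 cm (absent / mild) |
| 1.0 cm | 13 | 1, at 2.0 cm (absent / mild) |

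With a common lower bound, whichever one is chosen, no reading differs on any grid.

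Consequences for the derived variables, taking the diary data alone and assuming that presence follows the absent/mild grading:

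- **Presence and maximum severity.** A participant changes only if the largest reading over Days 1 to 7 is exactly 2.0 cm. If k of N participants in a group are in that position for a given reaction, the rate with that reaction, and its mild rate, is higher by k/N under the SAP bound. The documents give no value for k.
- **Any local reaction.** This changes only if the participant also has no other local reaction that counts.
- **Onset and duration.** SAP Section 3.1.2.1 takes onset as the first day with any severity and duration as resolution minus start plus 1. A 2.0 cm reading on an earlier or later day can therefore move either quantity, even when a larger reading occurs in between.
- **Moderate and severe rates.** These are unchanged, because the visible bands agree.

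In the combined analysis, a mild grade for the same event on the adverse event form would make the reaction present under either bound.

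**The case against.** The strongest counter-argument is that the threshold actually programmed may not be the one printed in centimetres. Both documents record size in a redacted unit, and redacted text follows every centimetre range in both tables. If grading runs on that unit and the hidden ranges match, no participant is graded differently and the conflict is only in wording. This stands. A reader might infer that a 2.0 cm reading will in fact be counted in one analysis and not in the other, and the documents do not establish that.

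A reader might also infer that Table 5 directly determines presence. It sits under the severity heading. Presence is derived in SAP Tables 3 and 4, which turn on a yes report and give no size cut-off. The link from a 2.0 cm measurement to presence runs through the sentence that includes absent among the analysis categories. That is a reasonable reading, but it is an inference.

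Finally, a reader might suppose that 2.0 cm readings are common because 2.0 cm is the smallest value that could grade as mild. With 0.5 cm steps it would be one of (5.0 − 2.0)/0.5 + 1 = 7 values graded mild under the SAP. With 0.1 cm steps it would be one of 31, and with 1.0 cm steps one of 4. Such counts say nothing about frequency, and neither document gives a distribution of readings.

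Loss of a sign in the PDF text is a weaker defence. The sign is missing from the mild cell in both SAP rows but survives in the moderate and severe cells of the same rows and in the protocol's mild cells.

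**Conclusion.** The visible lower bounds conflict and should be reconciled. Taken as printed, the disagreement is confined to readings of exactly 2.0 cm, for redness and swelling only. It can affect the any-reaction and mild rates, onset and duration.

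The consequence is minor. Primary safety is summarized descriptively with Clopper-Pearson intervals (protocol Section 9.3.2, SAP Section 6.1.2.1), and the fixed-sequence procedure covers only efficacy and immunogenicity hypotheses (protocol Section 9.1.4, SAP Section 5.1.3). The same rule would apply in both vaccine groups. The analysis on e-diary data alone is no independent safeguard, because it uses a scale modelled on Table 5.

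The conclusion rests on two assumptions: that the printed centimetre bounds are operative, and that presence follows the absent/mild grading. Its practical size cannot be estimated from the documents, and it is zero if the redacted device-unit ranges already agree and are what the programs use.

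**What to change.** Reconcile the mild lower bound for redness and for swelling so that SAP Table 5 and protocol Table 2 state the same one. Because the SAP declares alignment with Amendment 4 and no departure on this point, conforming Table 5 to the protocol is the natural route. The essential requirement is that the two agree.

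Then check the agreed bound against the device-unit ranges in both tables, and confirm that the programmed absent/mild cut-off and the presence variable in SAP Tables 3 and 4 use it, in both the combined and the e-diary-only analyses. A short sentence in SAP Section 3.1.2.1 saying how a measured size becomes a yes or a no would remove the remaining ambiguity.

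The cost is two table cells, one optional sentence and a programming check. No new data are needed, and sample size and testing are unaffected.
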